6.4.2 Secondary analysis

Secondary endpoints include the change in BNP, NYHA functional class, right ventricular basal diameter, TAPSE, emPHasis-10 score, and the number of participants with an escalation of routine clinical treatments for PAH during the trial.

The main analysis for each secondary endpoint will be performed for the FAS. Sensitivity analyses will be performed using the PPS1 and PPS2 analysis sets instead of FAS. Sensitivity analyses using worst case scenario and complete case analysis will be performed for the FAS.

6.4.2.1 BNP

Summary statistics (mean, standard deviation, median and range) of BNP (untransformed and log-transformed) and change from baseline for each visit will be presented by treatment group. Change in log-transformed value will be evaluated between the treatment groups using linear regression adjusted for the value at baseline and NYHA functional class (stratification variable). The difference with 95% CIs will be reported.

The BNP is expected to vary by NYHA functional class. An additional sensitivity analysis will be performed with the difference of log-transformed BNP between baseline and week 24 as the outcome, with the predictor variables being baseline log-transformed BNP, treatment group, baseline NYHA functional class, and an interaction term between treatment group and baseline NYHA functional class.

Missing data will be imputed in an analogous fashion to the primary outcome including sensitivity analyses to define the range of uncertainty imposed by missing data (worst case scenario and complete case analysis). The worst case scenario for BNP will be set to the highest value in the observed population.

6.4.2.2 NYHA functional class

Summary tabulations of the number and percentage of participants within each NYHA functional class for each visit will be presented by treatment group. NYHA functional class will be evaluated between the treatment groups using ordinal logistic regression adjusted for the baseline NYHA functional class (stratification variable). The odds ratio with 95% CIs will be reported.

Missing data will be imputed in an analogous fashion to the primary outcome including sensitivity analyses to define the range of uncertainty imposed by missing data (worst case scenario and complete case analysis) but for categorical variables [3]. The worst case scenario for NYHA functional class will be assumed to be IV.

6.4.2.3 Right ventricular basal diameter

Summary statistics (mean, standard deviation, median and range) of right ventricular basal diameter and change from baseline for each visit will be presented by treatment group. Change from baseline will be evaluated between the treatment groups using linear regression adjusted for the value at baseline and NYHA functional class (stratification variable). The difference with 95% CIs will be reported.

Missing data will be imputed in an analogous fashion to the primary outcome including sensitivity analyses to define the range of uncertainty imposed by missing data (worst case scenario and complete case analysis). The worst case scenario for right ventricular basal diameter will be set to the highest value in the observed population.

6.4.2.4 TAPSE

Summary statistics (mean, standard deviation, median and range) of TAPSE and change from baseline for each visit will be presented by treatment group. Change from baseline will be evaluated between the treatment groups using linear regression adjusted for the value at baseline and NYHA functional class (stratification variable). The difference with 95% CIs will be reported.

Missing data will be imputed in an analogous fashion to the primary outcome including sensitivity analyses to define the range of uncertainty imposed by missing data (worst case scenario and complete case analysis). The worst case scenario for TAPSE will be assumed to be zero.

6.4.2.5 EmPHasis-10 score

Summary statistics (mean, standard deviation, median and range) of emPHasis-10 score and change from baseline for each visit will be presented by treatment group. Change from baseline will be evaluated between the treatment groups using linear regression adjusted for the value at baseline and NYHA functional class (stratification variable). The difference with 95% CIs will be reported.

Missing data will be imputed in an analogous fashion to the primary outcome including sensitivity analyses to define the range of uncertainty imposed by missing data (worst case scenario and complete case analysis). The worst case scenario for emPHasis-10 score will be assumed to be 50.

6.4.2.6 Escalation of routine clinical treatments for PAH

Summary tabulations of the number and percentage of participants with an escalation of routine clinical treatments for PAH for each visit will be presented by treatment group.

Escalation of routine clinical treatments for PAH will be analyzed as a categorical variable (yes / no escalation). A Cochran-Mantel-Haenszel (CMH) test with adjustment for the stratification factor baseline NYHA functional class will be used to test the null hypothesis of no treatment effect during the trial for famotidine vs. placebo with regards to the proportion of subjects with an escalation of routine clinical treatments for PAH.

Odds ratios will be estimated from the CMH test together with the associated 95% confidence intervals (CIs) and corresponding p-values. The proportion per treatment arm will be displayed together with exact Clopper-Pearson 95% CIs. In addition, the common risk difference between famotidine and placebo will be provided, along with 95% confidence interval (stratified Newcombe confidence limits).

Missing data will be imputed in an analogous fashion to the primary outcome including sensitivity analyses to define the range of uncertainty imposed by missing data (worst case scenario and complete case analysis) but for categorical variables [3]. The worst case scenario for a participant will be assumed to have escalated PAH specific care.

6.4.3 Sub-study analysis

There are two sub-studies proposed for this trial. One sub-study involves cardiopulmonary exercise testing and the other sub-study involves invasive hemodynamic evaluation using right heart catheterization.

6.4.3.1 Cardiopulmonary exercise testing (CPET) sub-study

Summary statistics (mean, standard deviation, median and range) of CPET sub-study results and change from baseline for each visit will be presented by treatment group. The following metrics of the exercise response will be summarized:

- Peak VO₂ (mL/min)
- Peak Weight adjusted VO₂ (mL/kg/min)
- Ve/VCO₂ slope
- Achieved watts (watt)

6.4.3.2 Right heart catheterization (RHC) sub-study

Summary statistics (mean, standard deviation, median and range) of RHC sub-study results and change from baseline for each visit will be presented by treatment group. The following results will be summarized:

- Thermodilution stroke volume Index (mL/m²)
- Right atrial pressure (mmHg)
- Pulmonary Arterial Pressure Systolic (mmHg)
- Pulmonary Arterial Pressure Diastolic (mmHg)
- Mean Pulmonary Arterial Pressure (mmHg)
- Pulmonary capillary wedge pressure (mmHg)
- Thermodilution pulmonary vascular resistance (wood units)

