1.2 Objectives

Primary Objective:

To determine whether famotidine increases six-minute walk distance at 24 weeks in men and women with pulmonary arterial hypertension.

Secondary Objectives:

- To determine whether famotidine reduces BNP at 24 weeks
- To determine whether famotidine improves New York Heart Association (NYHA) functional class at 24 weeks
- To determine whether famotidine improves right ventricular morphology at 24 weeks including improved right ventricular dilation and TAPSE
- To determine whether famotidine improves health related quality of life as estimated by the emPHasis-10 score
- To determine whether famotidine decreases the need to escalate PAH focused care (increased diuretics, escalating doses of pulmonary vasodilators, and/or adding an additional pulmonary vasodilator)

Exercise sub-study:

- To determine whether famotidine increases maximal oxygen uptake in individuals with pulmonary arterial hypertension at 24 weeks
- To explore changes in other metrics of the exercise response (oxygen uptake, V_e/VCO_2 ratio, total achieved wattage) with famotidine relative to placebo over 24 weeks.

Right heart catheterization sub-study

- To determine whether famotidine increases stroke volume index at 24 weeks
- To explore whether famotidine is associated with differences in wedge pressure, right atrial pressure, and/or pulmonary vascular resistance at 24 weeks

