There are two sub-studies proposed for this trial. One sub-study involves cardiopulmonary exercise testing (CPET) and the other sub-study involves invasive hemodynamic evaluation using right heart catheterization (RHC). Understanding the relationship between therapy, exercise response, and invasive hemodynamic assessment is important for all pulmonary arterial hypertension (PAH) therapies and such studies are very common in trials of PAH-specific therapy. To date, nearly all therapeutic trials for participants with PAH have focused on medications intended to lower pulmonary vascular resistance and right heart afterload. Few studies have evaluated therapies intended to improve right heart fitness in the absence of changes in right heart afterload (“right heart targeted therapy”). Targeting myocardial histamine H2 receptors is one such therapy that is hypothesized to impact right heart fitness without

changing right heart afterload. While the two proposed sub-studies are powered to detect plausible, but large differences in exercise response or invasive hemodynamic markers, these studies are not powered to detect small to moderate differences. The co-primary intent of these sub-studies is to begin to understand appropriate end-points in trials of right heart targeted therapy. This more exploratory motivation is intended to complement but not supplant primary and secondary outcome measures including six-minute walk distance, BNP, and right ventricular structure and function by echocardiography in the current trial. Lessons learned from resting, exercise, and invasive measures will be used to inform subsequent trials of right heart targeted therapy using famotidine and/or other compounds. Exercise response and invasive hemodynamic differences in participants with pulmonary hypertension with and without exposure to famotidine will be studied.

Figure 2-1: Study design

All patients in the pulmonary vascular disease clinic are pre-screened using the electronic medical record.

Those interested in participation and eligible will be consented at their baseline visit. For most participants in the main study, all study assessments will occur during one study visit; however, sub-study participants and occasional main study participants may have study assessments on two or more different days. If this occurs then randomization will occur following the last baseline study assessment. Individuals who appear to violate inclusion or exclusion criteria as

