
Exercise sub-study:
 
To determine whether famotidine increases maximal oxygen uptake in individuals with pulmonary arterial hypertension at 24 weeks
 
To explore changes in other metrics of the exercise response (oxygen uptake, V_e/V_{CO_2} ratio, total achieved wattage) with famotidine relative to placebo over 24 weeks.
 
Right heart catheterization sub-study:
 
To determine whether famotidine increases stroke volume index at 24 weeks
 
To explore whether famotidine is associated with differences in wedge pressure, right atrial pressure, and/or pulmonary vascular resistance at 24 weeks
	
The primary analyses will be the change in oxygen consumption (VO_2) for the exercise sub-study and the change in stroke volume index (SVi) for the right heart catheterization sub-study conducted using the FAS.
 
Qualitative descriptions of other exercise and hemodynamic markers including mean, median, and distribution will be presented stratified by treatment group.
	
While the two proposed sub-studies are powered to detect plausible, but large differences in exercise response or invasive hemodynamic markers, these studies are not powered to detect small to moderate differences. The co-primary intent of these sub-studies is to begin to understand appropriate end-points in trials of right heart targeted therapy. This more exploratory motivation is intended to complement but not supplant primary and secondary outcome measures.

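### The SAP names primary analyses for the two sub-studies (VO2 and SVi) but pre-specifies only by-arm summaries, with no between-arm estimate or confidence interval

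*SAP*

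**What the plan says.** **Objectives.** SAP 1.2 words the lead objective of each sub-study as a comparison: "To determine whether famotidine increases stroke volume index at 24 weeks" and "To determine whether famotidine increases maximal oxygen uptake in individuals with pulmonary arterial hypertension at 24 weeks".

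**Named analyses.** SAP 3.1 (Table 3-1) states: "The primary analyses will be the change in oxygen consumption (VO_2) for the exercise sub-study", paired with "the change in stroke volume index (SVi) for the right heart catheterization sub-study conducted using the FAS". The next sentence covers the remaining markers: "Qualitative descriptions of other exercise and hemodynamic markers including mean, median, and distribution will be presented stratified by treatment group". Protocol Section 3 has the same structure, with the intent-to-treat population in place of the FAS.

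**Power.** SAP 2.1 introduces the sub-studies with: "While the two proposed sub-studies are powered to detect plausible, but large differences in exercise response or invasive hemodynamic markers". SAP 6.1 tabulates power for SVi and VO2 at 5 per group. Protocol 9.2 adds an SVi table at 10 per group after the catheterization sub-study was enlarged to 20.

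**Planned analysis.** SAP 6.4.3.1 plans "Summary statistics (mean, standard deviation, median and range) of CPET sub-study results", and 6.4.3.2 plans "Summary statistics (mean, standard deviation, median and range) of RHC sub-study results". Each adds change from baseline by treatment group. Neither mentions a model, a difference, a confidence interval or a test.

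**The concern.** Table 3-1 separates SVi and VO2 from the markers that are only to be described. Section 6.4.3 drops that separation and treats every marker alike. The two comparative objectives are therefore left without a pre-specified estimator, although participants undergo optional catheterization and exercise tests to address them.

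With 5 to 10 participants per arm, the estimator matters. Adjusting for baseline or not, and using absolute or weight-adjusted VO2 (6.4.3.1 lists both), can each change the result visibly. If these choices stay open, they may be made after unblinding.

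**Working it through.** **1. Is a between-arm analysis specified elsewhere?**
- Protocol 9.4 gives no sub-study method.
- SAP 6.2.1 sets two-sided 0.05 testing and promises confidence intervals for selected parameters as described in later sections. Section 6.4.3 describes none.
- SAP 6.2.3 says which covariates enter the model for continuous outcomes, but 6.4.3 calls for no model.
- SAP Section 7 lists departures from the protocol. A move to description for the sub-studies is not among them.
- By contrast, SAP 6.4.2.1 and 6.4.2.3 to 6.4.2.5 write out a regression, a difference and a 95% CI for each continuous secondary endpoint.

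**2. What analysis do the power tables presuppose?**

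Neither document states an SD for SVi or VO2, so the stated power cannot be reproduced from the plan's own inputs. As a consistency check, the SD was back-solved using a two-sided 0.05 two-sample t-test with equal arms: noncentrality = difference / (SD × sqrt(2/n)), df = 2n − 2.

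| Table | Differences | Stated power | Computed power |
|---|---|---|---|
| SVi, 5 per arm (SD 8.7) | 20, 15, 10, 5 | 0.87, 0.67, 0.36, 0.13 | 0.89, 0.67, 0.36, 0.13 |
| SVi, 10 per arm (SD 8.7) | 20, 15, 10, 5 | 0.99, 0.95, 0.68, 0.23 | 0.998, 0.95, 0.68, 0.23 |
| VO2, 5 per arm (SD 3.0) | 8, 4, 2 | 0.96, 0.46, 0.15 | 0.96, 0.46, 0.15 |

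One SVi SD (range 8.67 to 8.87) fits all eight SVi cells within 2 points, and one VO2 SD (2.92 to 3.07) fits all three VO2 cells. One-sided versions miss by 3 to 5 points. The tables therefore agree with a two-arm test that 6.4.3 never specifies.

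**3. How precise would the estimate be?**

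Unadjusted 95% CI half-width = t(0.975, 2n − 2) × SD × sqrt(2/n):
- SVi, 10 per arm: 2.101 × 8.7 × sqrt(0.2) = 8.2 mL/m2
- SVi, 5 per arm: 2.306 × 8.7 × sqrt(0.4) = 12.7 mL/m2
- VO2, 5 per arm: 2.306 × 3.0 × sqrt(0.4) = 4.4 mL/min/kg

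The documents do not say whether these SDs describe levels or changes. If they are level SDs, adjusting for a baseline value with correlation r multiplies the SD by sqrt(1 − r²) and costs one degree of freedom:
- SVi, 10 per arm, r = 0.5: 2.110 × 8.7 × 0.866 × 0.447 = 7.1; r = 0.7 (factor 0.714): 5.9
- VO2, 5 per arm, r = 0.5: 2.365 × 3.0 × 0.866 × 0.632 = 3.9; r = 0.7: 3.2

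Adding the NYHA stratum costs one more degree of freedom, with no credit taken for variance it might explain. SVi stays at 7.1 and 5.9 (t = 2.120); VO2 becomes 4.0 and 3.3 (t = 2.447).

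Under the same level-SD reading, the SD of change is SD × sqrt(2(1 − r)). The crude difference in mean change then has a half-width of 8.2 (r = 0.5) or 6.3 (r = 0.7) for SVi, and 4.4 or 3.4 for VO2. If the SDs are already SDs of change, the sqrt(1 − r²) factor does not apply.

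**The case against.** The strongest reply is that the sub-studies are exploratory. Table 3-1 files them under tertiary and exploratory objectives. SAP 2.1 gives a co-primary aim of learning which end-points suit later trials, and says the results complement the main outcomes. This stands: no formal test is required. It does not remove the mismatch, because the same table still names primary analyses and gives description only to the other markers.

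A reader might infer that, followed as written, the SAP cannot address the SVi and VO2 objectives at all. The documents do not support that. Section 6.4.3 reports the mean and SD of change by arm, and with the number per arm a crude difference and t-based interval follow by arithmetic. What is missing is a pre-specified, baseline-adjusted estimate.

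A second reply is that SAP 6.2.1 and 6.2.3 already imply the model. They suggest what the authors may have intended, and the defect may be only an incomplete cross-reference. But neither section assigns a model to SVi or VO2.

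Finally, the list of statistical outputs in SAP Section 10 was not in the text available for this review. The statement is therefore limited to what 6.4.3 and the other sections specify.

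**Conclusion.** The point holds as an inconsistency within the SAP: primary analyses are named and powered for the two sub-studies, but no between-arm estimate or interval is pre-specified for them. The half-widths above give its size. They rest on back-solved SDs of unstated type and on equal arms. Equal arms are not guaranteed, because sub-study participation is optional and randomization is stratified only by NYHA class. The adjusted figures also assume level SDs and correlations of 0.5 or 0.7. The gain from adjustment over the crude difference in change depends on r, and under the level-SD reading it is small at 0.7 (SVi 6.3 to 5.9).

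Importance is low to moderate. Nothing here touches the six-minute walk analysis or the secondary endpoints, and it would be wrong to read it as weakening them.

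**What to change.** In SAP 6.4.3.1 and 6.4.3.2, add a linear regression of the change from baseline to Week 24 on treatment group, for peak weight-adjusted VO2 (the unit family used in the power table) and for thermodilution SVi. Adjust for the baseline value and the NYHA stratum, as 6.2.3 requires. If the stratum is left out for the 10-person exercise set to save a degree of freedom, record that as an exception to 6.2.3.

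Report the difference with its 95% CI as an exploratory estimate. State that the analysis uses FAS participants with sub-study data, since 6.2.6 allows no imputation beyond what 6.4 describes. Keep the other markers descriptive.

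If the sponsor prefers pure description, the alternative is to reword the objectives and Table 3-1 to match and to list the change in Section 7. That would resolve the contradiction but give up the estimate.

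The cost is two extra regression outputs and a few sentences, with no added participants or procedures: a free improvement.

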6.4.4 Exploratory analysis

Pre-planned exploratory analysis: Etiology of PAH or sex may lead to effect modification in the relationship between study drug and outcomes. A subgroup analysis will be repeated for any group with at least 10 participants (e.g., men, women, toxin-induced PAH, idiopathic PAH, etc). The primary purpose of these analyses will be to inform subsequent trial design; however, if these individual analyses are reported it will be with the tempered inference informed by the fact that these sub-groups may not be balanced between active drug and placebo, are meant to be hypothesis generating only, and are underpowered as shown in the following table depicting the power to detect a minimally important difference in six-minute walk distance (assuming balanced groups which may not be true).

Alpha	Group size	Power
0.05	10	0.22
0.05	12	0.27
0.05	14	0.31
0.05	16	0.35
0.05	20	0.39

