6 STATISTICAL METHODS

6.1 Sample Size Justification

The primary endpoint is the change in six-minute walk distance (6MWD). The study was powered to detect a difference of 31.9 meters. A 31.9 meter improvement in 6MWD is well aligned with established thresholds for a minimally important difference in patient reported outcomes (Mathai SC, et al. Am J Respir Crit Care Med, 2012; 186(5):428-433). The 6MWD was chosen because it is a surrogate for patient-centered outcomes and was the primary endpoint in labeling trials for most of the medications used to treat pulmonary arterial hypertension (PAH).

Standard deviation in 6MWD among PAH participants with NYHA functional class II, III, or IV symptoms is 37.6 meters (national Pulmonary Hypertension Association Registry; unpublished data). As shown, the proposed sample size has adequate power (0.96) to detect a minimally important difference in 6MWD even with 10% attrition in the study sample (power, 0.94).

Table 6-1: Power to detect a minimally important difference in 6MWD (31.9 meters)

Alpha	Sample size per group	Power for the total sample size	Sample size per group with ~10% attrition	Power with attrition
0.05	20	0.74	18	0.69
0.05	40	0.96	36	0.94
0.05	60	0.99	54	0.99

The field is appropriately shifting toward larger event driven trials; however, we did not feel a larger event driven trial of famotidine was warranted at this juncture. The current proposal is the first randomized evaluation of this drug and this pathway in individuals with right heart failure and/or PAH and a smaller Phase II trial was felt to be a more appropriate next step.

For the RHC sub-study, the initial sample size was set at 10 participants based on the following power to detect large differences.

Size of difference	SV index (mL/m2)	Total sample size	n per group	power
Large	20	10	5	0.87
Medium-high	15	10	5	0.67
Medium-low	10	10	5	0.36
Small	5	10	5	0.13

For the exercise sub-study, the initial sample size was set at 10 participants based on the following power to detect large differences.

Size of difference	VO2 (mL/min/kg)	Total sample size	n per group	power
Large	8	10	5	0.96
Medium	4	10	5	0.46
Low	2	10	5	0.15

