6.2 General Statistical Methods

6.2.1 General Methods

All outputs will be incorporated into Microsoft Excel or Word files, sorted and labeled according to the International Conference on Harmonization (ICH) recommendations, and formatted to the appropriate page size(s).

Tabulations will be produced for appropriate demographic, baseline, efficacy and safety parameters. For categorical variables, summary tabulations of the number and percentage within each category (with a category for missing data) of the parameter will be presented. For continuous variables, the mean, median, standard deviation, minimum and maximum values will be presented.

Formal statistical hypothesis testing will be performed with all tests conducted at the 2-sided, 0.05 level of significance. Summary statistics will be presented, as well as 95% confidence intervals on selected parameters, as described in the sections below.

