6.2.5 Subgroups

No subgroups analyses are planned.

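### SAP 6.2.5 rules out subgroup analyses that 6.4.4 pre-plans, and 6.4.4 asks about effect modification without estimating any treatment-by-subgroup interaction

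*SAP*

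**What the plan says.** SAP 6.2.5 reads, in full, "No subgroups analyses are planned". SAP 6.4.4 opens with "Pre-planned exploratory analysis" and gives the reason: "Etiology of PAH or sex may lead to effect modification in the relationship between study drug and outcomes". The method is one sentence: "A subgroup analysis will be repeated for any group with at least 10 participants", with men, women and individual etiologies as examples.

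Section 6.4.4 also carries caveats. The main purpose is to inform the design of later trials. The subgroups may be unbalanced between arms. The results "are meant to be hypothesis generating only, and are underpowered". A table gives power of 0.22 to 0.39 at alpha 0.05 for group sizes of 10 to 20.

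No treatment-by-sex or treatment-by-etiology term appears anywhere in the SAP. An interaction term is specified once, for treatment by baseline NYHA class in a BNP sensitivity analysis (6.4.2.1). The general rule in 6.2.1 is "Formal statistical hypothesis testing will be performed with all tests conducted at the 2-sided, 0.05 level of significance", and 6.2.4 makes no multiplicity adjustment.

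**The concern.** There are two problems.

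- **The sections conflict.** Both are current text, and SAP section 7 (changes to planned analyses) does not resolve them. After unblinding, a subgroup result could be described as pre-planned under 6.4.4 or as unplanned under 6.2.5.
- **The method does not answer the question.** Effect modification is a difference between subgroup effects. Repeating the analysis inside each group yields a set of separate effects, with no estimate or interval for how far they differ. A reader who wants an answer on sex or etiology then has to compare the separate results by eye, and the easiest comparison is which groups reached significance. In small groups of unequal size, that comparison largely reflects group size.

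At stake is the next trial. If an apparent responder group guides its population, the choice could rest on chance. The primary estimate, the secondary analyses and the safety analyses of this trial are not affected.

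**Working it through.** **Inputs from the SAP.** Section 6.1: "The study was powered to detect a difference of 31.9 meters" and "Standard deviation in 6MWD among PAH participants with NYHA functional class II, III, or IV symptoms is 37.6 meters". Total 80, allocated 1:1 (2.2). Two-sided alpha 0.05 (6.2.1).

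**Assumptions.** The documents give no subgroup sizes. I use splits of 40/40, 50/30 and 60/20, and add 70/10 as the extreme because 10 is the SAP's minimum group size. Arms are balanced within each subgroup, as the 6.4.4 power table also assumes.

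**Step 1: reproduce the plan's own figures.** Power is that of a two-sided two-sample t-test (noncentral t) with n per arm and noncentrality 31.9 / (37.6 × √(2/n)).

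- Table 6-1, n per arm of 20, 18, 40, 36, 60, 54: I get 0.744, 0.696, 0.963, 0.944, 0.996, 0.992. The SAP gives 0.74, 0.69, 0.96, 0.94, 0.99, 0.99. They agree, apart from truncation in some cells.
- Table in 6.4.4, reading group size as the total of both arms, for 10, 12, 14, 16, 20: I get 0.220, 0.265, 0.309, 0.353, 0.435. The SAP gives 0.22, 0.27, 0.31, 0.35, 0.39. The first four rows agree. The last does not; 0.39 is the value for a total of 18 (0.394). This is a separate small slip and does not affect the point.

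**Step 2: disagreement between two subgroups with the same true effect.** With powers p1 and p2, the probability that exactly one is significant is p1(1 − p2) + p2(1 − p1). Half the design effect is 31.9 / 2 = 15.95 m. At no effect, p1 = p2 = 0.05.

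| Split | p1, p2 at 31.9 m | Disagree at 31.9 m | p1, p2 at 15.95 m | Disagree at 15.95 m | Disagree at 0 m |
|---|---|---|---|---|---|
| 40/40 | 0.744, 0.744 | 0.38 | 0.258, 0.258 | 0.38 | 0.095 |
| 50/30 | 0.836, 0.612 | 0.42 | 0.312, 0.202 | 0.39 | 0.095 |
| 60/20 | 0.898, 0.435 | 0.55 | 0.366, 0.146 | 0.40 | 0.095 |

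Worked line for 60/20 at 31.9 m: 0.898 × 0.565 + 0.435 × 0.102 = 0.507 + 0.044 = 0.55. At no effect: 2 × 0.05 × 0.95 = 0.095.

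Simulation (100,000 trials per scenario) gave the same disagreement rates for 40/40 and 60/20. In the same simulated trials, an interaction test at 0.05 falsely declared a subgroup difference in 4.9% to 5.1%.

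**Step 3: what an interaction term can detect.** For subgroups of total size N1 and N2, SE of the difference in effects = 37.6 × √(4/N1 + 4/N2). Power for a true difference of 31.9 m is approximately Φ(31.9/SE − 1.96).

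- 40/40: SE 16.82 m, power 0.48
- 60/20: SE 19.42 m, power 0.38
- 70/10: SE 25.42 m, power 0.24

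The difference detectable with 80% power, (1.96 + 0.84) × SE, is 47.1, 54.4 and 71.2 m respectively. An interaction test therefore holds the false-difference rate but will miss many real differences.

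**The case against.** The strongest reply is that 6.4.4 already says what a careful reader needs: few participants, possible imbalance, low power, hypothesis generating only, restrained inference if reported. The analysis being repeated gives an effect estimate with a 95% CI (6.4.1), and nothing in 6.4.4 says that subgroups will be compared by significance. Section 6.2.5 may have been meant for confirmatory subgroups only. An interaction model has costs too: six etiologies (6.4.1) in about 80 participants leave sparse cells, and its power is low.

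Much of this stands. The caveats do limit the harm. Comparison by significance is my assumption about how the results might be read; it is made plausible by the general testing rule and the alpha column in the 6.4.4 table, but it is not stated. The sparse cells and low power must shape the fix.

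Two things remain. The text of 6.2.5 is unqualified, so it conflicts with 6.4.4 whatever was intended. And a warning that each group is underpowered neither supplies an estimate of the between-group difference nor tells the reader that differing significance is common when the effect is uniform.

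**Conclusion.** The point holds as a contradiction between two sections and as a mismatch between question and method in 6.4.4. Its weight is moderate, because the analysis is exploratory and labelled so.

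The size is conditional. With two subgroups, SD 37.6 m, the assumed splits and the same true effect in both, separate tests would disagree with probability 0.38 to 0.55 at 31.9 m, about 0.38 to 0.40 at half that effect, and about 0.10 at no effect. These figures matter only if subgroups are compared by significance.

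A reader might infer more: that the plan prescribes such comparisons, or that it will often produce false responder groups. The documents do not support either. They prescribe no rule for comparing subgroups and warn against firm inference. The higher rates also need a real drug effect, which cannot be presumed in what SAP 6.1 describes as the first randomized evaluation of this drug in this setting.

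**What to change.** - **SAP 6.2.5:** replace the sentence with a reference to 6.4.4.
- **SAP 6.4.4, for 6MWD:** fit the primary model on the FAS with a treatment-by-sex term (and the sex main effect). Separately, fit it with a treatment-by-etiology term (and the etiology main effect), limited to etiologies with at least 10 participants. State beforehand whether smaller etiologies are pooled into one remaining category or left out of the interaction.
- **Reporting:** give the interaction estimates with 95% CIs beside the within-group estimates and CIs. Base any statement about effect modification on the interaction estimate, not on which groups reached significance.
- **Caveat to add:** interaction power is about 0.24 to 0.48 for a 31.9 m subgroup difference, so a non-significant interaction must not be read as evidence of a uniform effect.

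The cost is some SAP wording and two extra exploratory models. No new data, participants or visits are needed, and the primary analysis does not change. This is a cheap improvement. If the sponsor wants the same question answered for outcomes other than 6MWD, those need their own interaction models, because NYHA class and escalation are not analyzed by linear regression.
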